	Absolute change in lung allograft function	FEV1 and FVC
	Change in exercise capacity at 24 weeks	6-minute walk test

	Change in Quality of Life measurements at 24 weeks	EQ-5D-5L and SF-36 v2 questionnaires
	Change in Disease severity	ISHLT CLAD Stage
	Survival at 24 weeks	
Mechanistic	To identify changes in immune responses occurring in those responding to ECP therapy compared to non-responders to ECP and untreated controls to identify a beneficial mechanism of action	Immune cell phenotyping transcriptomics analysis of circulating leucocytes, serum cytokine analysis and measures of immune tolerance and apoptosis
	To determine if CLAD phenotype, clinical factors or immune and inflammatory markers in blood alone or in combination can predict likelihood to benefit from ECP	Regression models with responder/non-responder as an outcome and each potential clinical factor or biomarker included as a baseline covariate
Intervention	Nine cycles of ECP therapy administered at 0, +2, +4, +6, +8, +10, +12, +16 and +20 weeks. Each cycle consists of 2 ECP treatments on consecutive days	
Formulation, Dose & Route of Administration	Methoxsalen (UVADEX®) 20 micrograms/ml solution for blood fraction modification used in conjunction with the THERAKOS CELLEX Photopheresis System®	
	Administered via injection into the recirculation bag of the THERAKOS CELLEX Photopheresis System® prior to the photoactivation phase of ECP treatment	
	Dose 0.017mls methoxsalen per ml blood volume treated at ECP	
	Total dose administered is calculated according to buffy coat treatment volume per individual ECP treatment	

Contents

Clinical Trial Protocol	1
RESEARCH REFERENCE NUMBERS	2
PROTOCOL APPROVAL SIGNATURE PAGE.....	3
PROTOCOL ACCEPTANCE SIGNATURE PAGE.....	4
KEY TRIAL CONTACTS.....	5
TRIAL SUMMARY	10
GLOSSARY OF ABBREVIATIONS.....	17
1. BACKGROUND AND RATIONALE	20
1.1 Background.....	20
1.2 Rationale	21
1.3 Risk Assessment	22
2. OBJECTIVES AND OUTCOME MEASURES.....	23
2.1 Primary Objective.....	23
2.2 Secondary Objectives	23
2.3 Sub-Studies.....	23
2.3.1 Mechanistic Sub-study.....	23
2.3.2 Qualitative Sub-study.....	24
2.3.3 Health Economic Evaluation	24
3. TRIAL DESIGN	25
3.1 Summary of Trial Design	25
3.2 Trial Setting	25
3.3 Flow Charts of Study Design and Research Activity	26
3.3.1 Overview of Study Design	26
3.3.2 Flow Chart of Research Activity	27
3.4 Primary and secondary outcome measures/endpoints	28
3.4.1 Primary outcome measure	28
3.4.2 Secondary outcome measures.....	28

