3. TRIAL DESIGN

3.1 Summary of Trial Design

E-CLAD UK is a phase II, prospective, two-arm, randomised, open-label, multicentre clinical trial to evaluate the efficacy of ECP in stabilising lung function in lung transplant recipients with progressive CLAD.

Consenting patients who fulfil inclusion criteria will be randomised 1:1 to receive either SOC (control arm) or SOC plus a 20-week course of ECP. Patients randomised to receive ECP will be administered 18 treatments in 9 cycles of ECP over 20 weeks.

Follow up will be for a total of 24 weeks from commencing the intervention (4 weeks after the last cycle of ECP in the intervention arm). Follow up visits will be conducted for all participants at 4, 8, 12, 16, 20 and 24 weeks.

[figure not shown]
Participants in both arms will be assessed at 12 weeks to determine if they are responding to treatment. Participants who experience a >20% fall in FEV1 or FVC from baseline to 12 weeks **due to progressive CLAD** will be deemed non-responders.

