5.3.1 Randomisation details

Participants will be randomised to receive either ECP plus SOC (treatment arm) for 24 weeks or SOC (control arm) alone. Two variables will be used to achieve a balanced allocation of participants between the two trial arms:

- Site
- CLAD phenotype – RAS / BOS / mixed (For definitions see section 7)

Stratified block randomisation, targeting 1:1 allocation to the two trial arms, will be used. The trial is not blinded and so no arrangements will be required for unblinding.

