5.5.1 Participants in the ECP + SOC arm

At 12 weeks participants will be reviewed to assess response to treatment. Participants will have received 6 of the total 9 cycles of ECP planned in the treatment arm. Six cycles of ECP provides a meaningful treatment exposure and furthermore allows time for identification of participants who have rapidly progressive CLAD disease despite receiving an intensive short course of ECP therapy.

If at 12 weeks, either FEV1 or FVC has >20% decline from baseline measurements at trial entry due to progressive CLAD, they will be deemed non-responders to ECP plus SOC due to an insufficient therapeutic effect.

If a participant in the ECP plus SOC arm has a >20% fall in FEV1 or FVC from study baseline before their 12 week study visit and this is confirmed to be due to very rapidly progressive CLAD, then the site PI should assess the balance of risks in continuing with ECP treatment until 6 cycles have been completed or declaring the patient a non-responder before a meaningful exposure to ECP therapy has been achieved.

None of the potential rescue therapies that could be offered to participants discontinuing ECP therapy in the study have proven efficacy in treatment of CLAD in clinical trials and so this should be factored in any decision making by the site PI in identifying a participant as a non-responder before their 12 weeks study visit. A potential approach in those with a >20% fall in FEV1 or FVC before 12 weeks is to

prepare for access to a rescue treatment while also continuing to deliver ECP in the study so that this can commence promptly after the 12 weeks study visit.

In such situations, it is recommended that the site PI discusses the circumstances with the study CI to help ensure consistency of approach across centres in such cases.

Participants in the Newcastle mechanistic sub-study cohort who are classified as a non-responder at the 12 week assessment should still have their pre-ECP research blood sample collected even if they do not go on and have a 7th cycle of ECP treatment. This is to allow comparison with the baseline sample.

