5.7 Additional information and data collection at ECP visits

Participants allocated to receive ECP will attend their respective ECP unit for treatment at 0, 2, 4, 6, 8, 10, 12, 16, 20 weeks. At weeks 4, 8, 12, 16, 20 and 24, data regarding the patient's condition, lung function and changes to CLAD treatment will also be collected and recorded in the eCRF. Where the ECP treatment visit aligns with the follow up assessments (4, 8, 12, and 20 weeks), the research assessments should take place prior to the ECP treatment commencing.

Ideally sites should try to adhere to 14 days between ECP treatment cycles wherever possible. For cycles 1-7 and 28 days for cycles 8 and 9. Where this is not possible there should be a minimum of 10 days between ECP treatment cycles. and a maximum of 21 days between ECP treatment cycles.

The clinical assessments and blood samples taken at the ECP treatment visits are for clinical purposes to ensure it is safe to proceed with treatment and should take place prior to commencing the ECP treatment cycle as per usual clinical practice, matching those normally performed at each ECP unit. Any results necessitating alterations to the standard ECP protocol or deferment of treatment are to be recorded in the eCRF. There are no additional research assessments to be undertaken at each ECP treatment visit.

AE and SAE reporting and concomitant medication review should coincide with each trial visit. For weeks 2, 6 and 10 where patients receive ECP treatment but are not required for routine clinical assessment, details may be collected by the research team via a telephone call to the patient. For information on reporting AEs and SAEs, including those identified during the ECP procedure see section 8.2.

All participants in the ECP arm must be followed up for a minimum of 4 weeks after the last ECP treatment and any adverse events noted during this time reported as per section 9.

A data card comes as standard with each ECP treatment kit. This is inserted into the machine and collects data about the machine settings and the way the treatment went. For participants in the E-CLAD UK trial we are asking ECP teams to follow the steps below:

1. Record the ID of the ECP treatment kit on the participants treatment record – this links the participant to the kit that was used to treat them and the card that will contain the treatment data.

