8.2. Description of ECP Treatment

ECP therapy is performed using the THERAKOS™ CELLEX™ Photopheresis System® which is an automated enclosed system which separates a given volume of the patient's whole blood into plasma, red blood cell and white blood cell fractions. The red cells and some of the plasma is immediately returned to the patient while the white cells and remaining plasma is collected in a separate chamber. This collection process is repeated over a number of cycles. The buffy coat suspension of white blood cells is then treated with the photosensitising drug methoxsalen. After the cells have absorbed this drug, they are exposed to UVA light radiation, and then returned back into the patient's body. THERAKOS™ have agreed to provide CELLEX™ System Procedural Kits at a discounted rate to sites for trial procedures. Sites are also able to loan a CELLEX™ system from THERAKOS™ if required to meet ECP capacity as a result of trial recruitment.

In this trial, UVADEX® (methoxsalen) Solution will be the investigational drug. UVADEX® (methoxsalen) Sterile Solution will be injected directly into the Recirculation Bag of the extracorporeal circuit after completion of the buffy coat collection, immediately prior to initiating photo-activation. The dose of UVADEX® used to inoculate these cells will be calculated based on the standard treatment volume formula (see section 8.6). Heparin is the standard anticoagulant for use with the THERAKOS™ CELLEX™ Photopheresis System®. However, sites may use other anticoagulants such as citrate if routinely used as part of their standard local ECP protocol or if heparin is contraindicated for a patient. Patients in the ECP arm should have all of their treatments with the THERAKOS™ CELLEX™ Photopheresis System® at a set frequency over the course of 24 weeks. Each treatment takes about 2-3 hours to complete, and each cycle consists of 2 treatments performed on consecutive days. The treatment schedule in the study protocol means patients randomised to the ECP arm must receive their first cycle ideally within 14 days of their baseline visit, but no later than 28 days after baseline visit. Cycles are then performed every 2 weeks for the first 12 weeks and then every 4 weeks for the next 12 weeks. By 24 weeks after the baseline visit those who complete the study will have received 9 cycles of ECP equating to 18 individual treatments.

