10.2 Analysis Populations

All primary analyses of the primary and secondary outcome efficacy analyses will be carried out on an intention to treat basis in the full analysis population. The full analysis population will contain all patients recruited into the study (regardless of whether they were later found to be ineligible, allocated to the incorrect treatment, in violation of the protocol, etc.)

Safety analyses will be carried out similarly, in a safety population consisting of all patients recruited into the study.

Secondary efficacy analyses will be carried out in a per-protocol analysis population. The per-protocol analysis population will consist of the patients who completed a full-course of the treatment they were originally assigned (i.e. 12 weeks of treatment for the ECP plus SOC arm), as per the protocol.

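### The per-protocol set treats 12 weeks as a full ECP course, against 9 cycles to week 20 elsewhere, and its completer rule makes membership depend on outcome

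*Protocol*

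**What the plan says.** Section 10.2 assigns secondary efficacy analyses to a per-protocol population made up of "patients who completed a full-course of the treatment they were originally assigned (i.e. 12 weeks of treatment for the ECP plus SOC arm". It adds that this completion must accord with the protocol. No corresponding criterion is given for SOC. The primary analyses of the primary and secondary outcomes are by intention to treat.

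Other sections describe the ECP course differently:

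- Trial Summary: "Nine cycles of ECP therapy administered at 0, +2, +4, +6, +8, +10, +12, +16 and +20 weeks".
- Section 3.1: "Patients randomised to receive ECP will be administered 18 treatments in 9 cycles of ECP over 20 weeks".
- Section 5.5.1, on the 12-week review: "Participants will have received 6 of the total 9 cycles of ECP planned in the treatment arm".
- Section 8.2 spreads treatment over 24 weeks and says that "those who complete the study will have received 9 cycles of ECP equating to 18 individual treatments".
- Section 5.3.1: "Participants will be randomised to receive either ECP plus SOC (treatment arm) for 24 weeks or SOC (control arm) alone".

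On early failure, section 5.5.1 lets the site investigator, in a participant with very rapid progression before week 12, weigh continuing to 6 cycles against "declaring the patient a non-responder before a meaningful exposure to ECP therapy has been achieved". Section 5.12 says that withdrawal from the trial ends ECP. Section 5.5.3 counts non-responders as non-stabilised in the primary endpoint. Section 5.5.2 allows SOC participants with very rapid progression to be considered for rescue outside the trial.

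**The concern.** There are two linked problems. First, the protocol fixes a definition that conflicts with its own schedule: someone who has had two thirds of the planned cycles would be labelled as having completed a full course. This is not a detail left to the statistical analysis plan, because section 10.2 states the figure.

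Second, completing treatment is an event after randomisation that depends on how the participant fares. An ECP participant who dies, or who progresses and stops before week 12, cannot be a completer. The non-responders removed in this way are failures by the trial's own endpoint. SOC is continuing care with no natural course to complete, so it is unclear whether comparable SOC failures would be removed. Section 10.3.1 refers to secondary as well as primary analyses of the primary outcome, so the per-protocol comparison may well be read alongside the main result as support for it.

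**Working it through.** **1. Course length.** The Trial Summary schedule is weeks 0, 2, 4, 6, 8, 10, 12, 16 and 20.

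- Total: 9 cycles × 2 treatments = 18 treatments, last cycle at week 20. This reproduces section 3.1.
- Cycles before the week-12 assessment: 6, and 6/9 = 67%. This reproduces section 5.5.1.
- Cycles if the week-12 cycle is counted: 7, and 7/9 = 78%.

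Twelve weeks as a full course does not reproduce on either count. The choice between 6 and 7 also matters for membership. Section 5.4.5 places the response assessment before cycle 7, so a participant judged a non-responder at week 12 who then stops has 6 cycles. That participant is in the set if 12 weeks means 6 cycles and out of it if it means 7.

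**2. Effect of completer selection.** Let p be the true response rate in an arm and x the share of its non-responders excluded. The response rate among those kept is

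p / [p + (1 − p)(1 − x)].

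The rates of 30% (SOC) and 55% (ECP) come from section 10.1. The documents give no value for x, so x is an assumption, shown over 5–30%.

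*No true effect, 30% in both arms:*

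| x, ECP | x, SOC | ECP kept | SOC kept | Apparent difference |
|---|---|---|---|---|
| 5% | 0 | 0.30/0.965 = 31.1% | 30.0% | +1.1 points |
| 10% | 0 | 0.30/0.93 = 32.3% | 30.0% | +2.3 points |
| 20% | 0 | 0.30/0.86 = 34.9% | 30.0% | +4.9 points |
| 30% | 0 | 0.30/0.79 = 38.0% | 30.0% | +8.0 points |
| 20% | 20% | 34.9% | 34.9% | 0 |
| 10% | 30% | 32.3% | 38.0% | −5.7 points |

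For scale, 45 per arm at 30% response gives 45 × 0.70 = 31.5 non-responders, so x = 10–30% is roughly 3 to 9 people.

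*Design effect, 55% against 30%:* with no SOC exclusions, x = 10% in the ECP arm gives 0.55/0.955 = 57.6%, a difference of 27.6 points. With x = 30% it gives 0.55/0.865 = 63.6%, a difference of 33.6 points. The true difference is 25 points. Equal exclusion of 10–30% in both arms leaves 25.3 to 25.6 points.

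**3. Effect of requiring all 9 cycles.** Under the 12-week wording, participants who reach week 12 on ECP and are then judged non-responders can remain in the set (subject to the 6-or-7 question). A 9-cycle rule would remove everyone who stops at or after week 12 for progression as well. That raises x in the ECP arm and moves down the table.

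**The case against.** The strongest reply is that 12 weeks works as a minimum-exposure threshold. Section 5.5.1 regards six cycles as meaningful exposure, section 5.4.5 requires six before the formal assessment, and sections 1.3, 5.4.5 and 5.5.1 allow or encourage ECP to continue despite decline. On this reading few ECP failures are lost. Much of this stands: progression does not mean removal, and only those who stop before the threshold drop out. It does not rescue the wording, because a threshold is not a full course.

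A reader might infer that the rule necessarily favours ECP. The documents do not support that. Section 10.2 applies completion to the treatment originally assigned, which covers both arms, and SOC participants who leave for rescue must also be withdrawn (sections 5.5.2 and 5.5.3). The SOC criterion may properly be set in the statistical analysis plan, so its absence is not an error by itself. It means that the direction cannot be determined from the protocol.

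A reader might also infer from section 5.7, which gives 28 days for cycles 8 and 9 and then "and a maximum of 21 days between ECP treatment cycles", that every on-schedule participant breaches the protocol. The 10-to-21-day range is introduced for cases where the ideal spacing is not possible, so it reads as a fallback and on-schedule participants break nothing. What remains is that a fallback maximum shorter than the planned interval needs clarifying.

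Finally, the 24 weeks in section 5.3.1 can be read as time in the arm rather than length of ECP. The clear conflict is 12 against 20 weeks.

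**Conclusion.** The point holds in a limited form. The 12-week full course in section 10.2 contradicts the 9-cycle schedule, and the completer rule removes some participants because of their outcome. The secondary per-protocol comparison can therefore be biased. If only ECP non-responders are excluded, at an assumed 10–30%, the spurious gain with no true effect is about 2 to 8 points. It is zero if equal shares are excluded in both arms and turns against ECP if SOC loses more. A gain of 10 points would need a quarter of the whole ECP arm to be removed as early failures (0.30/0.75 = 40%). That is 0.25/0.70 = 36% of its non-responders, and nothing in the protocol points to so high a rate.

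The primary intention-to-treat analysis is unaffected. The change should be made because a stated rule is wrong and the remedy is only wording, not because the main conclusion is at risk.

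**What to change.** - Define the per-protocol set by eligibility and absence of major deviations not caused by outcome, with the same rule in both arms.
- State the ECP exposure criterion in cycles, making clear whether the week-12 cycle counts.
- Keep participants who stop because of death or protocol-defined non-response, and count them as non-responders.
- Do not simply replace 12 weeks with 20: requiring all 9 cycles would exclude more participants who stopped because they progressed.
- Reconcile the course-length statements in sections 10.2, 3.1, 5.3.1 and 8.2 and the Trial Summary, and clarify how the 21-day maximum in section 5.7 relates to the 28-day interval for cycles 8 and 9, before deviations are classified.

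The cost is revised wording in section 10.2, matching text in the statistical analysis plan, and reconciliation of the schedule sentences. It needs no new data and no change to the sample size or the primary analysis.

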10.3 Statistical Analyses

10.3.1 Analysis of the Primary Outcome Measure

The primary and secondary analyses of the primary outcome will be conducted using the augmented binary method (22). This will utilise a joint model of the change in FEV1 and FVC from baseline to 12 and 24 weeks, leveraging this to estimate the difference in probability of being a responder (no 'rapid decline' at 12 weeks and $\leq 10\%$ loss in FEV1 and FVC at 24 weeks) between the treatment arms. In addition to an estimated difference, the method will provide a confidence interval for the difference and a p-value for significance testing. The method allows covariates to be adjusted for: we will include the variables included in the stratified randomisation routine as covariates (CLAD phenotype and site).

Sensitivity analyses of the primary outcome will be conducted using a logistic regression model for the binary responder primary outcome, adjusting for CLAD phenotype and site. A second sensitivity analysis will include all participants who had $>20\%$ reduction from baseline in FEV1/FVC at 12 weeks as non-stabilised.

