Greer et al (14) reported a retrospective study of 64 CLAD patients over 4 years who, despite use of azithromycin continued to lose graft function and were treated with ECP. 54% responded to treatment with either an increase or <10% decline in FEV1. They found responders experienced a significant survival benefit with median survival being 401 days compared to 133 in non-responders. The RAS phenotype and rapid decliners were less likely to respond. The ECP regimen and schedule used in this study is very similar to that in the E-CLAD UK protocol.

Del Fante et al (15) reported a retrospective study of 48 patients with CLAD identified over 10 years who received ECP. They compared their outcomes with 58 CLAD patients not treated with ECP. The groups were not randomly allocated with many factors determining who received treatment; 30% had RAS and 70% BOS. They used an off-line or manual ECP protocol rather than an automated system as is planned in the E-CLAD UK study proposal. They showed a significant reduction in the rate of decline in FEV1 in the first 6 months after ECP was commenced compared to 6 months before ECP. 60% of patients treated with ECP stabilised their FEV1 defined as <10% decline within 6 months. There were no significant complications reported.

The exact mechanism of immunomodulation with ECP is not fully understood and published literature exploring this is limited to small uncontrolled studies. The proposed paradigm is that DNA cross-linking occurs in methoxsalen-treated leukocytes exposed to UV light causing apoptosis after return to the patient's circulation. The presence of the apoptotic cells then exerts effects on other immune cells driving the beneficial actions (16). Mechanistic studies of ECP in CLAD are extremely limited. A study of 5 patients with the BOS phenotype of CLAD, showed 3 who responded to ECP had a modest increase in regulatory T-lymphocytes (17). A further study in the BOS phenotype only showed a fall in pro-inflammatory cytokines and a reduction in donor-specific antibodies (18). There have been no studies which have systematically evaluated the immunological changes in circulating proteins, immune cell numbers, phenotype, and activation status to identify both mechanisms of action and potential markers which predict likelihood of a patient with CLAD responding to ECP.

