4.1 Inclusion Criteria

- Adults (≥ 16 years of age) with body weight ≥ 30 kg.
- Bilateral lung or heart and (bilateral) lung transplant recipients.
- Confirmed diagnosis of CLAD stages 1, 2 or 3 as per ISHLT 2019 consensus definition (see section 7 for definition).
- New CLAD diagnosis or prior diagnosis with evidence of current progressive disease.
- Exclusion of non-CLAD causes for decline in lung function by high-resolution computed tomography (HRCT) thorax and bronchoscopy +/- transbronchial biopsy within 12 weeks of first CLAD diagnoses.
- Adequate treatment of potential non-CLAD causes of a decline in lung function (e.g. acute cellular or acute humoral rejection, infections, airway anastomotic strictures and medical treatment for gastroesophageal reflux).
- Progressive decline in FEV1 ($\geq 10\%$) while on azithromycin for ≥ 6 weeks.
- Capacity to provide written informed consent.
- A minimum of 2 recorded FEV1 and FVC measurements (including home spirometry) obtained during the 26 weeks preceding consent*. Measurements must be at least 3 weeks apart with the last measurement at least 3 weeks prior to consent

* FEV1 and FVC values collected as part of routine clinic spirometry and research pulmonary function tests along with historical clinical spirometry data from medical records will be used. Ideally readings should be from the preceding 12 weeks but up to 26 weeks prior to consent is acceptable. These will ideally have been collected at clinical appointments, but home spirometry readings are also acceptable.

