10.1 Sample Size Calculation

Our proposed sample size is 90 patients. We used published evidence to underpin our sample size calculations. Todd et al reported changes in longitudinal lung function in 213 CLAD patients who did not receive ECP; 27% had a <10% loss in FEV1 within 6 months, equating to stabilisation. We assume conservatively that in the SOC arm, 30% patients will be responders. The three largest ECP in CLAD studies show 54-61% patients had <10% decline in FEV1 within 6 months; we therefore assume a 55% stabilisation rate in the ECP arm. With 90 patients randomised 1:1 between SOC and ECP arms, we would have 80% power (5% one-sided type I error rate) to detect a difference when the ECP arm has a 55% response rate and the SOC arm a 30% response rate. This calculation assumes Barnard's exact test is used in the analysis.

As the primary endpoint is a composite responder endpoint, our primary analysis will utilise the augmented binary method to test the difference in response rate as the primary analysis (see Section 10.10.2). Previous work has shown that the augmented binary method increases the power of the analysis equivalent to increasing the sample size by at least 35% without any inflation in the type 1 error-rate. Even allowing for 10% of patients dropping out, we are thus confident power will be above 85% for this analysis, and believe it is likely to be above 90%. Conservatively, for the augmented binary analysis we believe the maximum number of patients required to achieve 80% power is 68.

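### The covariates named for the primary model leave out baseline FEV1 and FVC, which gives up some precision in a 90-patient trial

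*Protocol*

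**What the plan says.** Section 10.3.1 describes the primary analysis as "a joint model of the change in FEV1 and FVC from baseline to 12 and 24 weeks", from which the difference in response probability is derived. It notes that the method permits covariate adjustment and then states that "we will include the variables included in the stratified randomisation routine as covariates (CLAD phenotype and site". The logistic sensitivity model is given the same two covariates. Baseline FEV1 and FVC enter only as the reference from which change is measured.

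Both values are available before allocation. Sections 5.2.4 and 5.4.1 schedule full pulmonary function tests at the baseline visit, and Section 5.3 places randomisation after baseline data collection. Earlier readings exist too. Section 4.1 requires "A minimum of 2 recorded FEV1 and FVC measurements (including home spirometry) obtained during the 26 weeks preceding consent", and Section 3.4.2 uses such readings for a rate of decline, for which it asks for at least 3 measurements.

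Section 10 refers full analysis detail to a separate statistical analysis plan, which is not at hand.

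**The concern.** When the outcome is a change from baseline, the baseline value is the usual first covariate. Measurement error in the baseline test enters the 12-week and 24-week changes directly, so change tends to be correlated with baseline. Entry also requires a recent fall in FEV1, which favours regression to the mean.

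Section 1.2 gives a further reason to look beyond the stratification factors. Of one cited retrospective ECP study it reports: "The RAS phenotype and rapid decliners were less likely to respond". That sentence names two predictors, and the primary model takes up the phenotype and not the rate of decline. In the health economic appendix (Section 16.3) the protocol does control the QALY comparison for baseline utility, to deal with small imbalances.

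What is at stake is efficiency. With about 45 patients per arm, variation that baseline lung function could explain stays in the residual and widens the confidence interval for the response difference.

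**Working it through.** **Inputs from Section 10.1.** "With 90 patients randomised 1:1 between SOC and ECP arms", so n = 45 per arm; "when the ECP arm has a 55% response rate and the SOC arm a 30% response rate"; "5% one-sided type I error rate", so z = 1.645; stated result "we would have 80% power". The same section allows 10% dropout and credits the augmented binary method with a gain equivalent to at least 35% more patients.

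**Input not in the documents.** R², the share of the variance in change explained by baseline FEV1 and FVC beyond site and phenotype. It is an assumption, shown from 0 to 0.20.

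**Step 1: the plan's own figure.** The pooled normal approximation is

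power = Φ{[d√n − z√(2p̄(1−p̄))] / √(p₀(1−p₀) + p₁(1−p₁))},

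with d = 0.25 and p̄ = 0.425. At n = 45 this is Φ{(1.677 − 1.645 × 0.699) / 0.676} = Φ(0.779) = 78.2%. The unpooled form, Φ{0.25/√(0.4575/45) − 1.645}, gives 79.8%. The stated 80% is reproduced to within 2 points. (Exact enumeration of Barnard's test, which the protocol names, gives 76.9%. That is a separate matter and is not used below.)

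**Step 2: the protocol's base for the primary method.** 90 × 0.90 = 81 evaluable; 81 × 1.35 = 109.4 effective patients, or 54.7 per arm. The pooled formula gives 84.9%, in line with the protocol's expectation of more than 85%.

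**Step 3: add baseline covariates.** Effective N = 109.4 / (1 − R²), put into the same formula:

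| Assumed R² | Effective N | Power |
|---|---|---|
| 0 | 109.4 | 84.9% |
| 0.05 | 115.1 | 86.5% |
| 0.10 | 121.5 | 88.1% |
| 0.20 | 136.7 | 91.2% |

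**Step 4: check by simulation.** 6,000 runs at N = 81 used a single continuous change dichotomised to 30% v 55% response, analysed with and without one baseline covariate. The variance of the estimated response difference rose by 0.6% at R² = 0. It fell by 5.8% at 0.05, 8.7% at 0.10 and 18.5% at 0.20. This supports the effective-N shortcut and shows that an uninformative covariate costs almost nothing. It is a one-component analogue; the trial's model has two measures at two times and a rapid-decline condition.

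**The case against.** The strongest reply is that covariate choice belongs to the statistical analysis plan. Section 10.3.1 does not say that its two covariates are the only ones, and the health economic appendix refers to adjustment factors specified in that plan. This stands in part: the list is not closed, and the unseen plan may extend it. But the protocol itself states the primary model and names its covariates, so the wording in 10.3.1 should match whatever is intended.

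A second reply is that adjusting for the stratification factors is sound and nothing is invalid. That stands in full. A reader might infer that a chance imbalance in baseline lung function would bias the estimate. The documents do not support that: under randomisation such imbalance is sampling error, already reflected in the confidence interval.

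Third, the gain is unproven. No R² is given. The remark on rapid decliners comes from a retrospective cohort in which everyone received ECP, and the entry criteria may narrow the range of prior slopes. This stands, and is why the result is a range that starts at zero.

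Fourth, a reader might infer that a prior slope is available for every participant. Eligible patients should have two earlier readings plus baseline. However, the footnote in Section 5.2.3 speaks of two readings including baseline, and Section 10.2 keeps patients later found ineligible. Home readings are also allowed, so a slope from about three points is noisy. The case for the slope is therefore weaker than that for the baseline values.

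**Conclusion.** The point holds as one of lost efficiency. The named covariates omit baseline FEV1 and FVC, which are scheduled for everyone before randomisation. On the protocol's own base, including them would lift power from about 85% to between 86.5% and 91% if they explain 5% to 20% of the remaining variance in change, and would leave it practically unchanged if they explain none. These figures rest on an assumed R², on the protocol's 35% gain and 10% dropout, and on the normal approximation. The change is worth making because the possible loss is so small, not because the present model is wrong.

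**What to change.** In Section 10.3.1, add baseline FEV1 and baseline FVC as prespecified covariates of the joint model, alongside CLAD phenotype and site, and carry the same wording into the statistical analysis plan.

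State that the covariate is the value measured before randomisation. Under Section 5.4.1, spirometry is repeated when the first ECP cycle falls more than 14 days after randomisation. That can happen only in the ECP arm, so using the repeat would condition on a post-randomisation value in one arm.

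The pre-randomisation FEV1 slope may be added where at least 3 readings exist, with a prespecified rule for patients without one.

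Leave the logistic sensitivity model as it is. With arm, four site terms and two phenotype terms it already has 7 parameters for about 38 expected responses (45 × 0.55 + 45 × 0.30 = 38.25), or about 5.5 responses per parameter.

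The cost is protocol and analysis-plan wording, no extra patient data, and a few model terms: at most 2 × 4 = 8 coefficients if both covariates enter all four modelled changes, or 12 with the slope. Section 5.3.3 wants the analysis plan signed off before the monitoring committee reviews unblinded data, so the change belongs before that point. If that point has passed and the change counts as a major amendment, that section's blinded-statistician approval applies.
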